14.6. Secondary Analysis

Non-inferiority of Test compared to Control with respect to the secondary endpoint of lens fit acceptance will be assessed on the safety population.

Let Y_1 and Y_2 denote the binary outcomes of lens fit acceptance (Yes/No) in left and right eyes, respectively, when wearing a study lens. Considering the correlation, ρ , between Y_1 and Y_2 , the distribution of the sum $Y = Y_1 + Y_2$ is obtained by the mixture of two variables. One of them follow a binomial distribution $Bin(2, p)$ with mixing probability $(1 - \rho)$ and the other one follows a modified Bernoulli distribution, $MBern(p)$, taking value 0 and 2 rather than conventional 0 and 1, with mixing probability ρ :

$$P(Y = y | p, \rho) = (1 - \rho)Bin(2, p)I_{A1} + \rho MBern(p)I_{A2},$$

where $I_{A1} = \{0, 1, 2\}$, $I_{A2} = \{0, 2\}$ and p is the probability of success (i.e., acceptable lens fitting).

To overcome the complexity of the mixture likelihood a latent variable Z_i , $i = 1, 2$ is introduced in the model to indicate in which component of the model the observation y_i , $i=1, 2$, belongs to, that is,

$$Z_i = \begin{cases} 1, & \text{if the observation belong to the } MBern(p), \\ 0, & \text{if the observation belong to the } Bin(2, p) \end{cases}$$

Clinical Study Protocol

Johnson & Johnson Vision Care, Inc.

The joint distribution of the augmented data $(Y_i, Z_i), i = 1, 2$, is given by

$$\begin{aligned} P(Y = y_i, Z = z_i | p, \rho) \\ = \rho^{z_i} p^{y_i z_i / 2} (1 - p)^{(2 - y_i) z_i / 2} (1 - \rho)^{1 - z_i} \binom{2}{y_i} p^{y_i(1 - z_i)} (1 - p)^{(2 - y_i)(1 - z_i)} \end{aligned}$$

The probability p links to the regression covariates through a logit transformation as follow:

$$\text{logit}(p) = \beta_0 + \beta_1 \text{lens} + \delta + \gamma$$

It is assumed that β_0 , β_1 and ρ to be independent with a non-informative prior $N(0, 1000)$ for β_0 and β_1 , and $\text{beta}(0.5, 0.5)$ for ρ . δ and γ are the subject-specific and site-specific random effects, respectively. We assume random subject effects are independent and identically distributed as $\delta \sim N(0, \sigma_{\text{subj}}^2)$ and random site effects are independent and identically distributed as $\gamma \sim N(0, \sigma_{\text{site}}^2)$. For the variances of random subject and site effects, an independent non-informative conjugate prior $\text{inverse-gamma}(0.001, 0.001)$ will be used. The Metropolis sampler algorithm as implemented in the SAS/STAT MCMC Procedure (SAS Institute Inc., 2015)³⁶ will be used to estimate the posterior distributions of the parameters (β_0 , β_1 , ρ). Inferences will be made based on a posterior credible interval for the relevant parameters.

Hypothesis Testing

The null and alternative hypotheses for testing non-inferiority of Test relative to Control are as follows:

$$\begin{aligned} H_0: p_T - p_C \leq -0.1 \\ H_1: p_T - p_C > -0.1, \end{aligned}$$

where p_T and p_C are the probability of success (i.e., acceptable lens fitting) for Test lens and Control lens, respectively. Non-inferiority will be declared if the posterior probability $p(p_T - p_C > -0.1 | \text{data}) \geq .975$.

In the case of all eyes have an acceptable lens fit (i.e., zero unacceptable lens fit), a Bayesian hierarchical model accounting for zero event problem will be considered (Chen & McGee, 2008).³⁷ Details of this model will be provided in the stand-alone SAP.

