14. STATISTICAL METHODS

This section is a general outline of the statistical methods that will be implemented in this clinical trial. More details will be included in the stand-alone Statistical Analysis Plan (SAP). The standalone SAP will be finalized and signed prior the database lock and unmasking.

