14.2. Sample Size Justification

This study was designed and powered to demonstrate non-inferiority of the Test lens (EMO-200) compared to the Control lens (EMO-118) with respect to monocular distance logMAR visual acuity under bright HLHC and lens fit acceptance after 10-minute lens settling period. The ample size was calculated for both the primary and secondary endpoints to achieve a minimum statistical power of 80% using a 2-sided type I error of $\alpha=0.05$ based on historical data from [REDACTED] [REDACTED] was a 2×2 crossover study with two study lenses (EMO-116 and EMO-118). In [REDACTED] all eyes had acceptable lens fit. Table 6 below presents the descriptive statistics of monocular logMAR visual acuity under bright HLHC at fitting observed from [REDACTED].

Clinical Study Protocol

Johnson & Johnson Vision Care, Inc.

Table 6: Descriptive Summary of Monocular LogMAR Visual Acuity Post Lens-Fitting from [REDACTED] – Per Protocol Subjects

	EMO-116	EMO-118
Number of eyes	50	50
Mean (SD)	-0.03 (0.098)	0.01 (0.082)

SD = standard deviation

Monocular Distance logMAR Visual Acuity

The sample size estimate for monocular distance logMAR visual acuity was calculated using a linear mixed model-based power analysis method³³. The model included lens, period, and lens wear sequence as fixed effects. An unstructured (UN) covariance matrix was used to model the residual errors between measurements within the same subject and eye across study periods. It was assumed there was no difference between the Test and Control lenses since the two study lenses have not been evaluated in the same study previously. Sample size estimation was carried out using an approximation of the power of an F-test derived from the non-centrality parameter calculated from the observed F statistic of the linear mixed model. Below is the variance-covariance matrix used in the sample size calculation for monocular logMAR visual acuity.

Subject intercept: 0.003087

The UN covariance matrix:
$$\begin{bmatrix} 0.004953 & -0.00076 \\ -0.00076 & 0.005157 \end{bmatrix}$$

Lens Fit Acceptance

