Acceptable lens fit is a binary response as $Y = 1$ if a subject eye has an acceptable fit and $Y = 0$ otherwise. Indicated by the historical data from [REDACTED] there was no unacceptable lens fitting for both study lenses. Assuming no difference between study lenses and a correlation of 0.80 between left and right eyes within the same subject and period; and a correlation of 0.50 between measurements within the same subject across periods, a total of 2000 replicating trials were simulated with a reference (Control lens) rate of 95% (worse-case scenario) for lens fit acceptance. Given the rare event binary outcome of fit acceptance (i.e., the number of unacceptable fit is very small), each replicated sample was analyzed using a Bayesian beta-binomial model with correlated binary data (Diniza et al; 2010).³⁴ Sample size was estimated to achieve a minimal statistical power of 80% with a non-inferiority margin of -10% (Test – Control). Table 7 summarizes the required number of subjects for each of the primary and secondary endpoints to achieve a minimum of 80% statistical power with a 2-sided type I error of 0.05.

Table 7: Sample Size and Power for the Primary and Secondary Endpoints

Endpoints	Test/Margin	Sample size	Power
Monocular LogMAR VA	Non-inferiority (0.05)	28	92%

Clinical Study Protocol

Johnson & Johnson Vision Care, Inc.

Lens Fit Acceptance	Non-inferiority (-10%)	56	81%
---------------------	------------------------	----	-----

As indicated in Table 7 above, the sample size chosen for this study was primarily driven by lens fit acceptance in order to achieve a statistical power of at least 80% for both primary and secondary endpoints. The plan is to enroll approximately 67 subjects with a target of 56 to complete the study.

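### The augmented likelihood printed for lens fit drops the {0,2} restriction; coded as printed, it overstates the eye correlation and costs about 3 to 6 points of power at the 95% planning rate

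*Combined protocol and SAP*

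**What the plan says.** Section 14.6 (Secondary Analysis) lets Y be the number of acceptable eyes, 0, 1 or 2, for a child wearing a given lens. With probability 1 − rho, Y follows Bin(2, p). With probability rho it follows a modified Bernoulli, MBern(p), "taking value 0 and 2 rather than conventional 0 and 1". The mixture display carries this restriction through an indicator on {0, 2}.

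The section then changes form: "To overcome the complexity of the mixture likelihood a latent variable" Z is introduced, with Z = 1 for the MBern component and Z = 0 for the binomial. "The joint distribution of the augmented data" is printed next, with no indicator. The logit of p contains the lens effect plus two terms that "are the subject-specific and site-specific random effects, respectively". Estimation uses "The Metropolis sampler algorithm as implemented in the SAS/STAT MCMC Procedure". Non-inferiority is declared if the posterior probability that p_T − p_C exceeds −0.1 is at least 0.975.

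Section 2.3 requires both the primary and the secondary hypothesis to be met. Section 14.2 sized the trial on this endpoint: 56 completers for 81% power (Table 7), "with a reference (Control lens) rate of 95% (worse-case scenario) for lens fit acceptance". Section 14 leaves further detail to a stand-alone SAP.

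**The concern.** The two displays in Section 14.6 disagree about a child with one acceptable and one unacceptable eye. Under the mixture, such a child can only come from the binomial component. Under the augmented density, the child can also come from MBern, and with substantial weight.

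Discordant pairs are the observations that show the eyes are not perfectly correlated. If the likelihood lets a high-rho component explain them, rho is overestimated. Each child then contributes less effective information and the posterior for p_T − p_C widens. The augmented form is offered as the way round the mixture likelihood and is followed directly by the sampler, so a programmer could well code it. The endpoint must be met and was planned with one point of power above the 80% minimum.

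**Working it through.** **Algebra.** The printed density is

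rho^z · p^(yz/2) · (1−p)^((2−y)z/2) · (1−rho)^(1−z) · C(2,y) · p^(y(1−z)) · (1−p)^((2−y)(1−z)).

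- z = 0 gives (1−rho)·Bin(2, p), which is correct and sums to 1 − rho.
- z = 1, y = 0 gives rho(1−p), and z = 1, y = 2 gives rho·p. Both are correct and together sum to rho.
- z = 1, y = 1 gives 2·rho·sqrt(p(1−p)). It should be 0.

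The total is 1 + 2·rho·sqrt(p(1−p)). At p = 0.95, sqrt(0.0475) = 0.2179, so the total is 1.087, 1.218 and 1.349 for rho = 0.2, 0.5 and 0.8.

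**Why rho is pulled up.** The correct probability of a discordant pair is 2(1−rho)p(1−p), which falls to zero as rho approaches 1. At p = 0.95 and rho = 0.8 it is 0.2 × 2 × 0.0475 = 0.019. The printed form adds 0.349, giving 0.368. Because sqrt(p(1−p)) exceeds p(1−p), the printed value rises with rho.

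**Inputs (Section 14.2).** Equal rates of 95%, eye correlation 0.80, cross-period correlation 0.50, margin −10%, N = 56. Priors and the 0.975 rule are from Section 14.6, with N(0, 1000) read as variance 1000.

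**The plan's 81%.** A normal approximation comes close if the analysis ignores the cross-period correlation that is present in the data.

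- Variance of a child's two-eye mean: 0.0475 × (1 + 0.8)/2 = 0.04275.
- Standard error the analysis assumes: sqrt(2 × 0.04275/56) = 0.0391.
- True standard error: sqrt(2 × (0.04275 − 0.5 × 0.0475)/56) = 0.0261.
- Power: Phi((0.1 − 1.96 × 0.0391)/0.0261) = Phi(0.90), or 81.6%.

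Simulation with the correct likelihood and no random effects gives 79.1% to 80.5%.

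**Correct against printed form.** Both forms were applied to the same simulated trials using grid posteriors. Trials with no unacceptable fit were counted as successes.

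| Setting | Correct | Printed | Loss (points) |
|---|---|---|---|
| No random effects, 95%, common-source data (20,000 trials) | 80.5% | 75.1% | 5.4 (SE 0.2) |
| Same, copula data (20,000) | 79.2% | 74.2% | 5.0 (SE 0.2) |
| No random effects, 97% | 92.2% | 90.0% | 2.2 |
| No random effects, 98% | 96.7% | 95.4% | 1.3 |
| No random effects, 99% | 99.6% | 99.3% | 0.3 |
| Subject and site effects, 95%, p at zero effects (1,600) | 99.4% | 95.9% | 3.4 (SE 0.5) |
| Same, p averaged over the effects (1,600) | 86.5% | 80.6% | 5.9 (SE 0.6) |
| Subject and site effects, 98% (400) | – | – | 0.5 (p at zero effects) or 3.3 (averaged) (SE 0.4, 0.9) |

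The full-model rows assume 5 sites (Section 4.3 gives 4 to 6) and no true site variation. Section 14.6 does not say which p is meant, so both readings are shown. Separate simulations without random effects gave losses of 3.6, 4.5 and 5.2 points at the planning values. With a subject effect only, the loss was 2.0 to 2.6 points (p at zero effects) or 5.4 to 5.9 (averaged). Mean posterior rho without random effects was 0.73 (correct) and 0.94 (printed).

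**At the margin (95% against 85%), planning correlations, no random effects.** Declarations of non-inferiority went from 2.5% to 1.8% or from 1.1% to 0.7%, depending on the data generator. With a subject effect and averaged p, they went from 4.4% to 2.9% (800 trials). The printed form declared non-inferiority less often in each case.

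**A decision that flips.** Counts are both/one/neither eye acceptable. With Control 53/1/2 and Test 52/1/3 and no random effects, the posterior probability is 0.980 (pass) under the correct form and 0.973 (fail) as printed.

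**The case against.** The restriction is stated in the same section. MBern is defined on {0, 2}, and Z = 1 is defined as membership of MBern, so the pair (y = 1, z = 1) lies outside the stated support. On that reading the augmented density is right at every admissible point and only an indicator was not repeated. The harm needs a programmer to code the second display without the first. Section 14 is an outline, and the stand-alone SAP may already be correct. Table 7 gives no sign of miscoding: its 81% agrees with the correct likelihood under the model without random effects. That is weak evidence, because the full model with averaged p gives 80.6% under the printed form.

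The size can also be questioned. The 95% rate is labelled a worst case, and in the historical study "all eyes had acceptable lens fit". The loss shrinks as the rate rises and vanishes if no child has discordant eyes. Under the full Section 14.6 model even the printed form keeps 80.6% or 95.9% power at 95%. The direction is conservative, and flips are not all one way: of 20,000 common-source trials, 1,321 passed only with the correct form and 245 only with the printed one.

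These points limit the consequence and are accepted. They do not repair the display, which is called a joint distribution, stands complete without the restriction, and is the form offered for computation. At the 95% rate, 87% of simulated trials contained a discordant child, so the condition for harm would usually be met.

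**Conclusion.** The augmented density in Section 14.6 is wrong as written. It gives mass to an outcome that the section's own definition excludes, and it does not sum to 1. Coded literally, it overstates rho and makes the lens-fit test conservative. At the 95% planning rate with 56 children and the planning correlations, the loss is about 3 to 6 points of power in most variants, and 2.0 to 2.6 points with a subject effect only and p taken at zero effects. At a 98% rate it is about 1 point without random effects. The mass error is exact algebra. The power figures depend on the data generator, the random-effects structure and the reading of p.

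The consequence arises only if the printed form is coded and at least one child has discordant eyes. No inflation of false non-inferiority from the error was seen, and this is not a finding that the specified analysis falls below 80% power. It should be fixed because the endpoint must be met and the correction costs almost nothing.

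**What to change.** Multiply the printed joint density by I(y ∈ {0, 2})^z. Equivalently, set Z = 0 whenever exactly one eye is acceptable, or code the marginal mixture directly and drop Z. Moving the binomial coefficient to the z = 0 term alone is not enough: it leaves rho·sqrt(p(1−p)) at y = 1, z = 1 and gave the same power as the printed form.

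Carry the corrected form into the stand-alone SAP and its program before database lock, and confirm that the planning simulation used the correct mixture. The cost is one line in one formula and a check of two pieces of code. This error by itself requires no change to sample size, data collection or Table 7.

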Clinical Phase	Clinical trial phase: confirmatory Design control phase: confirmatory phase, phase 3
Trial Registration	The study will be registered on clinicaltrial.gov by the Sponsor.
Test Article(s)	
Investigational Products:
 
 • Test: EMO-200 • Control: EMO-118 
Both lenses are Daily disposable soft contact lenses (SCL) made in senofilcon A material.

Wear and Replacement Schedules	
Wear Schedule: Daily wear
 
Replacement Schedule: Daily disposable
 
This is a non-dispensing study. Subjects will wear both test articles during one visit. The order of contact lens type received will be randomized.

Objectives	
To compare visual acuity and lens fit performance of EMO-200 with EMO-118 lens.
 
Primary Objective: To demonstrate that visual acuity of EMO-200 lens is non-inferior to EMO-118 lens.
 
Secondary Objective: To demonstrate that lens fit performance of EMO-200 lens is non-inferior to EMO-118 lens.

Study Endpoints	
Primary endpoint:
 
 • Monocular distance (4 m) logMAR visual acuity under bright lighting conditions with a high luminance, high contrast chart (bright HLHC), measured per [REDACTED] and [REDACTED] 
Secondary endpoints:
 
 • Lens fit acceptance, measured per [REDACTED] 
Other endpoints:
 
 • Monocular distance (4 m) logMAR visual acuity under dim lighting conditions with a low luminance, high contrast chart (dim LLHC), measured per [REDACTED] and [REDACTED] • Monocular distance (4 m) logMAR visual acuity under bright lighting conditions with a high luminance, low contrast chart (bright HLLC), measured per [REDACTED] and [REDACTED]

Clinical Study Protocol

Johnson & Johnson Vision Care, Inc.

	
 • Lens centration and movement characteristics, measured per [REDACTED] • Slit lamp findings, measured per [REDACTED] • Subject reported ocular symptoms, measured per [REDACTED] • Pupil diameter (mm), measured per [REDACTED]

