5. TEST ARTICLE ALLOCATION AND MASKING

5.1. Test Article Allocation

The study lenses will be worn in a bilateral and random fashion using a 2x2 crossover design with 2 lens types and 2 periods. Two lens types will be fit at one study visit. Using a computer-generated randomization scheme provided by the study biostatistician, each subject will randomly be assigned to one of two unique sequences of the two lens types (Test/Control, or Control/Test).

Permuted block randomization will be used to avoid bias in the assignment of subjects to treatment, and to enhance the validity of statistical comparisons across treatment groups. Each block will contain two different lens trial sequences. The randomization scheme will be generated using the PROC PLAN procedure in Statistical Analysis System (SAS) Software Version 9.4 or higher (SAS Institute, Cary, NC, USA).³²

The clinical site will follow the randomization scheme provided and will complete enrollment according to the randomization list and will not pre-select or assign subjects.

Randomization shall be performed at Visit 1. The following must have occurred prior to randomization:

- Informed consent must have been obtained.
- The subject must have met all eligibility criteria.
- The subject's screening and baseline information must have been collected.

When dispensing test articles, the following steps shall be followed to maintain randomization codes:

1. Investigator or designee (documented on the Delegation Log) will consult the lens fitting schedule to obtain the test article assignment for that subject prior to dispensing.
2. Investigator or designee will record the subject's number on the appropriate line of the lens fitting schedule.
3. Investigator or designee will pull the appropriate test articles from the study supply. All test articles that are opened, whether dispensed (placed/fit on eye or dispensed outside the clinical site) or not, must be recorded on the Test Article Accountability Log in the "Dispensed" section.

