1.7	Subjective Best Sphere Refraction	
Perform subjective best sphere refraction with a phoropter (adopt the maximum plus to maximum visual acuity (MPMVA) approach and use the duo-chrome test for binocular balancing) and record the resultant distance visual acuity (OD, OS) to the nearest letter.
 
Note: The endpoint criterion for the duo-chrome test is the lens power at which the red and green sides of the chart appear to be equally distinct. However, if the subject's response changes from "red" to "green" with only a 0.25 D change in power and no report that the two sides appear to be equally sharp, the refraction endpoint should be the lens power that leave the red chart sharper.
	
1.8	Cover Test	Perform distance and near cover-uncover test to rule out the presence of strabismus.	
1.9	Slit Lamp Findings	
Slit Lamp Classification Scale per ISO 11980 will be used to grade the findings.
 
Note: Except for subjects with Grade 2 palpebral conjunctival observations that are eligible to be enrolled, if any other slit lamp finding (per ISO 11980) is graded as 2 or worse, the subject may not continue at this time, but may return up to one additional time to determine eligibility. If the subject is discontinued from the study, Final Evaluation must be completed.
 
If the clearance of the fluorescein needs to be expedited, preservative-free rewetting drops or saline may be instilled.
	
1.10	Screen for Corneal Distortion	Examine the keratometer mires or corneal topography Placido ring pattern to rule out corneal distortion.	
1.11	Pupil Diameter	Measure pupil diameter under the following two lighting conditions:	

Clinical Study Protocol
Johnson & Johnson Vision Care, Inc.

Visit 1: Baseline			
Step	Procedure	Details	[REDACTED]
		
 • dim illumination (1.4-1.6 lux, or -0.8--0.6 EV), 4 meters away from a low luminance (2.5-2.8 cd/m², or 4.3-4.5 EV), high contrast chart (LLHC, with a mesopic filter); • bright illumination (686-788 lux, or 8.1-8.3 EV), 4 meters away from a high luminance (181-208 cd/m², or 10.5-10.7 EV), high contrast chart (HLHC). 
One measurement per eye, per condition.
 
Note: Subjects with pupil diameter less than 2mm under the biring illumination in either eye will be discontinued from the study.
	[REDACTED]

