14.5. Primary Analysis

Non-inferiority of Test compared to Control with respect to the primary endpoint of monocular logMAR visual acuity will be assessed on the Per-protocol population (PP).

Clinical Study Protocol

Johnson & Johnson Vision Care, Inc.

Monocular Distance logMAR Visual Acuity (VA)

Monocular distance logMAR VA under bright HLHC will be analyzed using a linear mixed model to compare the Test and Control lenses after a 10-minute lens setting period. The model will include lens type, lens sequence, and period as fixed effects. Other subject characteristics such as age, gender and race will be included as fixed covariates when appropriate. Site and subject will be included in the model as random effects (G-side). The covariance of residuals between measurements on the same eye across periods within the same subject (R-side) will be modeled using Unstructured (UN) covariance structure. If the model does not converge, then other covariance structures, such as compound Symmetry (CS) covariance structure, will be considered. The Kenward and Roger method (Kenward & Roger, 1997)³⁵ will be used for the denominator degree of freedom.

Hypothesis Testing

The null and alternative hypotheses for testing non-inferiority of the Test lens relative to the Control lens with respect to logMAR visual acuity are as follows:

$$\begin{aligned} H_0: \mu_T - \mu_C &\geq 0.05 \\ H_A: \mu_T - \mu_C &< 0.05 \end{aligned}$$

Where, μ_T represents the mean logMAR VA score for the Test lens and μ_C represents the mean logMAR VA score for the Control lens. Non-inferiority will be declared if the upper bound of the 2-sided 95% confidence interval of the difference (Test – Control) is less than 0.05.

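### The fit-acceptance model leaves out period, which the acuity model includes; any bias needs unequal sequences and is small, and a period term is free to add

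*Combined protocol and SAP*

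**What the plan says.** Section 14.6 says: "The probability p links to the regression covariates through a logit transformation as follow". It then gives the linear predictor for acceptable fit as logit(p) = β0 + β1·lens + δ + γ, where "δ and γ are the subject-specific and site-specific random effects, respectively". Priors are listed for β0, β1, the between-eye parameter ρ and the two variances. Nothing in the model refers to period or sequence.

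For acuity, section 14.5 says: "The model will include lens type, lens sequence, and period as fixed effects". The model used to size the acuity endpoint in section 14.2 has the same three terms. The documents do not explain why the two endpoints are treated differently.

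On allocation, section 5.1 says that "each subject will randomly be assigned to one of two unique sequences of the two lens types", using permuted blocks: "Each block will contain two different lens trial sequences". Block length and any stratification by site are not stated.

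Three other places bear on the point:
- Section 2.3 requires both the acuity and the fit hypothesis to be met.
- Section 14.2 (Table 7) sizes the study on fit: 56 children, 81% power, margin −10%.
- Section 7.2, step 1.16, keeps a child whose first lens fits unacceptably until the second lens has been assessed for fit.

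**The concern.** In a 2x2 crossover each lens is worn first by one group and second by the other, so period is a design factor and is normally in the model. Here the two wears are not alike. The baseline slit-lamp examination comes before lens 1 only, and step 1.9 allows that "If the clearance of the fluorescein needs to be expedited, preservative-free rewetting drops or saline may be instilled". Spectacle wearers and uncorrected children may enrol (section 3.1), so for some of them lens 1 may be the first lens ever worn. Lens movement is one of the fit criteria (section 2.2). A difference in fit between first and second lens is therefore conceivable, although the documents give no estimate of one.

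Fit acceptance is a required hypothesis, and its stated power is only 1 point above the 80% target. If the plan says nothing about period, a later decision to adjust for it, or not, would be a discretionary choice on an endpoint that decides the study.

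**Working it through.** **Step 1. The plan's own figure.** Inputs from section 14.2: 56 children, 95% acceptance on both lenses, correlation 0.80 between eyes and 0.50 across periods, margin −0.10. The decision rule, posterior probability at least .975, is from section 14.6. Simulating 28/28 and applying the section 14.6 likelihood by numerical integration, without the random subject and site effects, gave power of 79.1% and 79.8% under two data generators (3,000 trials each). That is within 2 points of the stated 81%. With a random subject effect, power was 91.5–92% when p was averaged over subjects, so the version without it is the main reference below.

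**Step 2. When a period effect cancels.** Let τ be the true Test − Control difference and π the first-lens minus second-lens difference in acceptance. Let n1 children get Test first and n2 get Control first, with n = n1 + n2.
- Test first: expected Test − Control = τ + π.
- Control first: expected Test − Control = τ − π.
- Mean over all children = τ + π(n1 − n2)/n.

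If n1 = n2, π drops out. Otherwise the bias is about π(n1 − n2)/n, and its sign depends on which sequence is larger.

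**Step 3. Size.** The values of π and of the imbalance are assumptions; n = 56.

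| Imbalance | π = 5 points | π = 10 points |
|---|---|---|
| 2 (29/27) | 5 × 2/56 = 0.18 | 10 × 2/56 = 0.36 |
| 4 (30/26) | 5 × 4/56 = 0.36 | 10 × 4/56 = 0.71 |
| 6 (31/25) | 5 × 6/56 = 0.54 | 10 × 6/56 = 1.07 |

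**Step 4. False non-inferiority claims at a true difference of −0.10, no period term** (6,000 trials per row; Monte Carlo standard error √(0.02 × 0.98/6000) ≈ 0.2 point at 2%).

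| Split and period effect | Mean difference | Claims, no subject effect | Claims, subject effect, p averaged over subjects |
|---|---|---|---|
| 28/28, 0 points | −0.0994 | 2.0% | 5.1% |
| 28/28, 5 points | −0.0989 | 2.1% | 4.9% |
| 28/28, 10 points | −0.0993 | 1.9% | 4.2% |
| Imbalance 6, 5 points, against Test | −0.1044 | 1.6% | 3.7% |
| Imbalance 6, 5 points, favouring Test | −0.0942 | 2.5% | 5.4% |
| Imbalance 6, 10 points, against Test | −0.1101 | 1.1% | 2.3% |
| Imbalance 6, 10 points, favouring Test | −0.0889 | 2.9% | 6.7% |

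The balanced rows show no bias and no inflation. In the unequal rows the period-adjusted means were −0.0991, −0.0996, −0.0995 and −0.0995. The shifts are therefore about 0.53, 0.54, 1.06 and 1.06 points, as step 3 predicts.

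**Step 5. With and without a period term** (section 14.6 likelihood, no subject or site effect, 800 trials per setting; standard error about √(0.78 × 0.22/800) ≈ 1.5 points for power).
- 28/28, 5-point effect: power 78.1% and 78.8% for the two versions, no material difference.
- 31/25 and 25/31, 5-point effect: without the term, power was 71.2% in one direction and 83.0% in the other; with it, about 78% in both.
- 25/31, 5-point effect, type I error: 3.0% without, 2.5% with. The standard error is √(0.025 × 0.975/800) ≈ 0.6 point, so these are not distinguishable.
- No period effect: the two versions had power of 80.9% and 81.6%; at 98% acceptance, 96.5% and 97.1%. The term has no measurable cost.

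**Step 6. Sequence as well.** Intercept, lens, period and sequence are four coefficients for four sequence-by-period cells, so the fixed part is saturated. Each lens is seen in only two of the four period-by-sequence combinations. With a flat-prior sequence coefficient, and p_T and p_C averaged over combinations that were never observed, power fell to about 48%.

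**The case against.** The case for leaving the model alone is strong on size. Permuted blocks containing both sequences hold imbalance down, and a first-lens fit failure does not remove the second-lens reading. No document reports a period effect on fit. The earlier crossover cited in section 14.2 had no unacceptable fits, and 95% is called a worst case, so a 5-point period effect equals the whole failure rate in that worst case. With so few failures, a sparse model is reasonable. All of this stands, and it is why the point is minor.

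Two parts do not stand. Sparseness argues against a sequence coefficient, but not against one period term, which cost nothing measurable. Section 14 does call itself an outline and leaves detail to a stand-alone SAP. But section 14.6 already fixes the likelihood, predictor, priors, sampler and decision rule, and defers only the zero-event model. Nor is balance guaranteed: fit is analysed on the safety population, which can include a child who leaves after one lens.

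A reader might infer that any first-lens/second-lens difference inflates the error rate or biases the comparison. The planned allocation does not support that: the effect cancels at equal sequences, and an imbalance can make the test stricter as easily as more lenient. A reader might also infer from section 14.5 that sequence belongs in the fit model. Step 6 shows why that does not carry over to a rare binary outcome.

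**Conclusion.** The inconsistency is real and unexplained, but its effect is small. Under equal sequences nothing is lost. Under an assumed 5-point period effect and an assumed imbalance of 4 to 6 in 56, the bias is 0.36 to 0.54 point in either direction, against a 10-point margin. Power at an imbalance of 6 then depends on which sequence happens to be larger, and a period term removes that dependence.

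The limits are these. The period effect and imbalance are not in the documents. Site effects were not simulated. The 81% was matched only with the random subject effect left out. How p_T and p_C are defined once that effect is in the model is a separate question and matters more: with no period effect, false claims were about 35% with the subject effect set at zero and about 5% when averaged over subjects.

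Rating: minor, a free improvement.

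**What to change.** In section 14.6, or in the stand-alone SAP before database lock and unmasking, write logit(p) = β0 + β1·lens + β2·period + δ + γ, with the same type of prior for β2 as for β1. State that p_T and p_C are equal-weight averages over the two periods, and apply the −0.10 rule to their difference. Do not add a flat-prior sequence coefficient; one sentence should say why sequence is in the acuity model but not here.

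The cost is one line of text and one line of code. No new data or children are needed, and no loss of power was measurable in the settings checked.
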